Public Health
England

NHS
Chelsea and Westminster Hospital
NHS Foundation Trust

PrEP Impact Trial

TRIAL PROTOCOL

Protocol Title:	PrEP Impact Trial: A pragmatic health technology assessment of PrEP and implementation
Short Title:	PrEP Impact Trial
Protocol Number	SSCR104
Version	3.0, 19 Jun 2018
Chief Investigator:	[name]
Sponsor:	Chelsea and Westminster Hospital NHS Foundation Trust

GCP Compliance Statement

This trial will be conducted in compliance with the protocol, the principles that have their origin in the Declaration of Helsinki 2013 and all applicable regulatory requirements

Synopsis

Title:	PrEP Impact Trial: A pragmatic health technology assessment of PrEP and implementation
Short title:	PrEP Impact Trial
Protocol Number:	SSCR104
Trial drug:	Tenofovir Disoproxil (TD)/ Emtricitabine (FTC) The generic product, manufactured by Mylan, is bio-equivalent to the branded product (Truvada) and is provided off label for event-based dosing in accordance with established practice supported by clinical evidence.
Background and rationale:	New prevention efforts are required to reduce the estimated 4,700 incident HIV infections occurring annually in England, of which 2,800 occur among men who have sex with men (MSM). Tenofovir containing regimens used as HIV PrEP are highly effective at reducing HIV acquisition. The data from the PROUD trial in the UK reinforced the evidence for efficacy, though the relatively small sample prevented the results being generalised to all GU clinic attendees and left unanswered key questions about large-scale use of PrEP. The PrEP Impact Trial aims to address these outstanding questions about PrEP, eligibility, uptake and duration of use of PrEP through expanding the assessment to the scale required to obtain sufficient data. In addition the new trial will assess under real world conditions the impact of PrEP on new HIV diagnoses and on sexually transmitted infections, compared to historical controls. The results will inform service commissioners about how to support clinical and cost effective PrEP access in the future.
Aim:	To test the hypothesis that consensus estimates using best available data on PrEP need, uptake and duration of use are correct and, if not, provide accurate measures across the complexity of the population likely to benefit from this medicinal product. This is required to determine the commissioning of future access to PrEP.
Objectives:	
 1. To measure PrEP-eligibility, PrEP-uptake, duration of PrEP-eligibility and duration of PrEP-use (PrEP prevention care continuum) among Genitourinary Medicine (GUM) clinic attendees, 2. To determine whether or not incident HIV infections in trial participants are due to non-adherence or biological failure, 3. To measure change over time in HIV diagnoses and incidence rate in those at high HIV risk,

	
4. To measure change over time in bacterial STI diagnoses and incidence rate in those at high HIV risk,
 
5. To measure the PrEP 'prevention care continuum' by clinic throughput and in different regions.

Design:	Prospective open label health technology assessment.
Treatment of participants:	
Two prophylaxis schedules for PrEP will be available for MSM and trans-women populations: daily or event-based dosing (EBD).
 
EBD cannot be recommended for heterosexuals and transgender men as this technology has not been assessed for effectiveness, nor for participants with active hepatitis B infection due to the risk of hepatic flares on withdrawal. Therefore, daily PrEP will be offered to these participants.

Methodology:	
Potentially eligible participants will be identified following a clinical risk assessment primarily during routine sexual health clinic visits, but may be contacted following review of the clinic database. Other methods such as outreach activities, and through community organisations and social media, may be used to identify potentially eligible patients for referral to a local genitourinary medicine (GUM) clinic.
 
Participants who consent to enrol in the trial will be allocated a trial ID and be prescribed PrEP at a GUM clinic. Routine clinic records and the standard data routinely extracted into the national GUM Clinic Activity Dataset (GUMCAD) database will be used to capture clinical and prescribing data. The subject ID will be linked to relevant GUMCAD record using the subject ID number, SOUNDINDEX code and semi-anonymised GUM clinic number in the trial database. Adverse events will be reported using the 'Yellow card' system and logged in the trial database for central monitoring. Dispensing data will also be collected for central monitoring.
 
In line with national guidance and the evidence from efficacy trials, at each visit participants will be offered PrEP as part of an active risk reduction intervention, including health education and safer sex promotion, to reduce and modify high risk behaviour. This may include the provision of free condoms, behaviour change interventions, other biomedical interventions such as post-exposure prophylaxis where relevant, the diagnosis and treatment of sexually transmitted infections (STIs), and regular HIV testing.
 
Participants who are starting PrEP are recommended to have a one month safety check (which can be done in person, on the phone or via email) and then

	quarterly visits depending on ongoing risk, with clinical risk assessments and tests performed according to the visit schedule and recommended clinical practice.
Planned Sample Size:	13,000 participants
Participant population:	
The participant populations for this trial will be men and women attending GUM clinics who belong to one of three populations recognised to be at high risk for HIV, namely:
 
A. Men (cisgender and transgender) and transgender women who:
 
 1. Have sex with men 2. Have had an HIV negative test during an earlier episode of care in the preceding year 3. Report condomless intercourse (excluding oral) in the previous 3 months 4. Affirm their likelihood of having condomless intercourse (excluding oral) in the next 3 months 
B. HIV negative partners of an HIV positive person when:
 
 1. The HIV positive partner is not known to be virally suppressed (<200 copies/ml for 6 months or more) 2. Condomless intercourse (excluding oral) is anticipated before treatment of the HIV positive partner takes effect 
C. HIV negative persons who:
 
 1. Are clinically assessed and considered to be at similar high risk of HIV acquisition as those with a serodiscordant partner who is not known to be virally suppressed
Inclusion Criteria:	
Participants will be considered eligible for trial enrolment if they fulfil all the following individual eligibility criteria:
 
 1) Belong to one of the three high HIV risk populations described above; 2) Aged 16 years or over (no upper limit); 3) Considered to be HIV negative on the day of enrolment; 4) Willing and able to provide informed consent; 5) Willing to adhere to the recommended PrEP regimen; 6) Willing to re-attend the trial clinic at appropriate intervals for risk assessment
Exclusion Criteria	Participants will not be considered eligible for trial enrolment if they fulfil any of the following exclusion criteria:

	
 1) An acute viral illness that could be due to HIV seroconversion 2) Any contraindication to Tenofovir Disoproxil (TD)/ Emtricitabine (FTC)- according to the current package insert or SmPC
Number of Prescribing Centres:	Prescribers that meet agreed site participation standards will be selected from the 232 Genitourinary Medicine (GUM) clinics in England. The decision to include a prescriber will be made by the sponsor. The aim is to establish a wide geographical spread of trial sites with prescribers in urban and rural settings; in high, medium and low throughput clinics; and in clinics with predominantly MSM and non-MSM eligible populations.
Duration of the trial:	4.5 years (33 month recruitment period)
Dose and Route of Administration:	
Drug: Tenofovir Disoproxil (TD)/ Emtricitabine (FTC). Each film-coated tablet contains 200 mg of emtricitabine and 245 mg of tenofovir disoproxil (as maleate).
 
Regimen: Daily or event-based regimens (EBD). Daily involves taking 245 mg TD and 200mg FTC once a day. EBD will involve taking a double dose before sex and then single doses 24 and 48 hours after the initial dose. EBD is not recommended for heterosexual men, heterosexual women, and transgender men due to lack of trial efficacy data to support this regimen in these risk groups.
 
Route of administration: Oral

Trial Outcomes:	
 1. Proportion of GUM clinic attendees that meet PrEP eligibility criteria, the proportion that is prescribed PrEP per year and the duration of PrEP-eligibility and PrEP-use among users. 2. HIV and STIs: 
 a. HIV diagnoses reported by sites and identified through the national surveillance dataset b. STI diagnoses (gonorrhoea, chlamydia, syphilis and hepatitis C) reported in the national surveillance dataset 3. Adverse Events 
 a. Serious suspected adverse drug reactions reported using the yellow card system b. Antiretroviral resistance associated mutations in participants with incident HIV infection

GENERAL TRIAL INFORMATION**Chief Investigator:**

[name]
Chelsea & Westminster NHS Foundation Trust
[name],
[name]

Sponsor:

Chelsea & Westminster NHS Foundation Trust
[name],
[name]

Funder:

NHS England

Trial management:

Chelsea & Westminster NHS Foundation Trust
[name],
[name]

Email: [contact]

Medical Expertise:

[name] - Public Health England
Email: [contact]

[name] - University of Manchester
Email: [contact]

[figure not shown]
[name] - Public Health England
Email: [contact]

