4. TRIAL DESIGN

4.1 Trial drug regimen

The combination drug to be used in this trial is Tenofovir Disoproxil (TD)/ Emtricitabine (FTC), a generic form manufactured by Mylan. Both drugs are nucleot/side analogue HIV-1 reverse transcriptase inhibitors. The drug is UK licensed and used off label for event-based dosing in accordance with established practice supported by clinical evidence. It is bio-equivalent to the branded product (Truvada). The drug should be taken orally in accordance with the drug SmPC and current package insert. All participants will be supplied with the current version of the information leaflet commissioned by the BASHH MSM Special Interest Group (Appendix 1), in line with established practice.

Two treatment schedules will be available: daily and event-based dosing (EBD). The decision to take one regimen or the other will be decided following risk assessment and discussion between the prescribing clinician and The information leaflet (Appendix 1) contains text and pictures to describe how to take this regimen in the context of a single sex act and several sex acts over a number of days. EBD is not recommended for heterosexual men, heterosexual women, and transgender men as this regimen has not been evaluated in clinical trials in these risk groups.

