4.7.2 Medications that are not recommended for concomitant use

Site investigators should familiarise themselves with the SmPC for the trial product being used. As per the SmPC for Tenofovir Disoproxil (TD)/ Emtricitabine (FTC), the following medications should not be taken concomitantly with the trial drug:

- Drugs containing Emtricitabine or Tenofovir Disoproxil Fumarate (TD) including Atripla, Emtriva and Viread,
- Adefovir dipoxil,
- Lamivudine and other cytidine analogues,
- Didanosine,
- Cidofovir and other medical products that compete for active tubular secretion,
- Drugs that reduce renal function.

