4.7.3 Medications to be used with caution

Co-administration of PrEP with drugs that are eliminated by active tubular secretion may increase concentrations of Tenofovir Disoproxil (TD)/ Emtricitabine (FTC) or the co-administered drug. Such medications should be used with caution as per the SmPC for Tenofovir Disoproxil (TD)/ Emtricitabine (FTC) and may require more frequent monitoring of serum creatinine.

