 - 3-monthly 4th generation venous blood HIV test +/- POCT
 - 3-monthly STI screen for MSM [*as per BASHH 2014 MSM guidance*]; STI screen as appropriate for heterosexuals
 - Urinalysis every visit (further investigation if protein 1+ or more)
 - Annual creatinine/eGFR (more frequent if abnormal at baseline or proteinuria or >50 or on concomitant medications that are relevant to renal function)

Note: POCT useful on the day of starting, and at any visit if risks were taken during a period when PrEP was not as per national guidelines on HIV testing.

Dosing

Event-based dosing for a single sex act comprises two tablets 2–24 hours before sex, one tablet 24 hours (22–26 hours) after the first dose, and another tablet 48 hours (46–50 hours) after the first dose.

- Heterosexuals/trans men/trans women: event-based dosing has not been investigated in heterosexuals; based on this and pharmacokinetic concerns, we recommend daily PrEP and do not recommend event-based PrEP. In the absence of other data, trans women and trans men should also be offered daily PrEP
- MSM: as daily and event-based PrEP showed similar efficacy, event-based PrEP should be discussed and offered.

Assessing adherence and adverse events

- Assessment 1-month after commencing PrEP (face-to-face, telephone, email or text) provides the opportunity to review adherence, adverse events and HIV/STI window periods
- Reasons for non-adherence including adverse events should be elicited and documented at each follow-up visit. Additional support, practical or psychological may be required. Adverse events should be reported through the yellow card scheme at <https://yellowcard.mhra.gov.uk/>

Coding and data collection

- Until processes for formal coding and outcomes monitoring are established, we strongly encourage clinics to collect data locally for visits when PrEP is started, continued or interrupted (including when interrupted because no longer at risk)

Online purchase of generic tenofovir/emtricitabine

- It is legal for a patient to obtain 3 months of generic drug via the internet for personal use
- A prescription is not required but some sellers may request this.
- The website www.iwantprepnw.co.uk has been set up by community advocates to provide information about PrEP and links to sellers. Sellers are added to the site only when generic drug has been purchased with no problems and therapeutic drug monitoring (TDM) has been carried out in at least one person showing presence of the drug.

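### The protocol and its annexed guidance conflict on event-based dosing for trans women, and Sections 4.7.2 and 4.7.3 conflict on drugs that share active tubular secretion

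*Combined protocol and SAP*

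**What the plan says.** **Event-based dosing, protocol body.** The synopsis entry on treatment of participants says "Two prophylaxis schedules for PrEP will be available for MSM and trans-women populations". It then says "EBD cannot be recommended for heterosexuals and transgender men as this technology has not been assessed for effectiveness", and continues "nor for participants with active hepatitis B infection due to the risk of hepatic flares on withdrawal". It concludes that daily PrEP will be offered to the groups so restricted. Section 4.1 has its own list: "EBD is not recommended for heterosexual men, heterosexual women, and transgender men as this regimen has not been evaluated in clinical trials". The synopsis row on dose and route lists the same three groups. Neither list names trans women or hepatitis B.

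**Event-based dosing, Appendix 2.** The Dosing part has one entry for heterosexuals, trans men and trans women together. It recommends the daily schedule, advises against the event-based one, and ends "In the absence of other data, trans women and trans men should also be offered daily PrEP". Earlier in the same guidance, under recommended tests, on-demand use is advised against in chronic hepatitis B.

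**Interacting drugs.** Section 4.7.2 introduces a list of medicines that are not to be taken with the trial drug. One item is "Cidofovir and other medical products that compete for active tubular secretion". Section 4.7.3 deals with drugs eliminated by active tubular secretion and says "Such medications should be used with caution as per the SmPC", adding that creatinine may need checking more often.

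**Hepatitis B.** Section 4.7.5 covers participants with active hepatitis B who are on, or need, treatment for it. It lets them use the daily schedule where the drug is indicated for that treatment, under a hepatologist.

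**The concern.** These are instructions that a prescriber would act on. If two places in one bound document give different answers for the same person, two sites can each follow the protocol and still manage that person differently. All Level-3 GUM clinics in England that meet the site criteria may take part (Section 3.1). Monitoring is central, with site visits only if triggered (Section 9.1), so divergent handling might not be noticed. What is at stake is participant safety and uniform conduct.

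**Working it through.** No figure in the plan depends on this point, so there is no arithmetic. The check sets side by side every visible statement on event-based dosing and on tubular secretion.

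1. **Trans women.** The synopsis makes both schedules available to them. The dose row and Section 4.1 do not exclude them, so the protocol body agrees with itself. Appendix 2 differs. Being offered daily PrEP need not by itself mean that event-based dosing is discouraged, but the entry in which that sentence stands is headed with trans women and advises against event-based use. The next entry, for MSM, says event-based use should be discussed and offered. The contrast leaves little doubt about the guidance's intent. The appendix is in the protocol's table of contents and is titled as practical guidance for healthcare workers. No visible sentence ranks it below the body or explains a deliberate departure from it. **Result: conflict.**

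2. **Tubular secretion.** Section 4.7.2 speaks of products that compete for secretion, Section 4.7.3 of drugs eliminated by it. The wording differs, but a drug eliminated by this route can also compete for it, and no rule separates the two classes. One section says not to combine; the next says combine with caution. Both cite the SmPC, so that citation does not settle the matter within the protocol. Section 4.7.3 is in working use: the baseline renal assessment in Section 5.4.1 refers to it for more frequent monitoring. **Result: conflict, within the protocol body and in adjacent sections.**

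3. **Active hepatitis B.** Two differences appear.
   - The synopsis says daily PrEP will be offered, without condition. Section 4.7.5 ties daily use to a hepatitis B treatment indication. It may be meant only for those on or needing treatment, but it does not say what applies to the others.
   - The restriction on event-based dosing is in the synopsis treatment entry (active infection) and in Appendix 2 (chronic infection), but is missing from the lists in the dose row and Section 4.1.

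   **Result: an inconsistency and an omission.** No passage says that event-based dosing may be used in hepatitis B.

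**The case against.** **On trans women,** the best reply is that Appendix 2 reproduces an external position statement. It covers matters such as online purchase and interim local data collection, and the visible body text never sends prescribers to it; Section 4.1 cites Appendix 1. On that view the body governs. The reply has force, and a single sentence on precedence could settle this item. But no such sentence is visible, and the protocol relies repeatedly on established practice, which guidance of this kind describes.

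**On tubular secretion,** the SmPC may separate the two classes, and investigators are told to know it. That cannot be checked from these documents. The overlap in the protocol's own wording remains.

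**On hepatitis B,** a reader might infer that Section 4.1 permits event-based dosing there. It does not; it is silent. Its sentence on how the regimen is chosen is also broken off in the text available, and the Appendix 1 leaflet it cites could not be checked. Section 5.4.1 requires hepatitis B status to be confirmed at baseline, and Section 4.7.5 mentions only daily use. This objection stands, so the item is a lesser one.

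**On the analyses,** a reader might infer that regimen becomes confounded with clinic in the duration, adherence and seroconversion results. The documents do not support this:
- Section 8.3 plans no comparison of regimens.
- Regimen is not among the covariates named in Section 8.1 or the model states in Section 8.3.
- Between-clinic variation in duration is modelled with a random effect.
- Seroconversions are investigated individually (Sections 4.6 and 5.7).
- The co-medication conflict has no bearing on regimen choice.

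A clinic random effect does not repair conflicting instructions, but no bias follows from them on what is written.

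**Conclusion.** The point holds in this form: two conflicts in prescribing instructions (trans women; tubular secretion) and one lesser inconsistency (hepatitis B). The tubular-secretion conflict is the firmer in its location, because both statements are in the protocol's own text. The trans-women conflict depends on Appendix 2 carrying some authority, which the documents leave open.

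The size cannot be given. The documents do not state how many of the planned 13,000 participants are trans women, have active hepatitis B or take the drugs concerned. It would also go too far to say that everyone in these groups is affected, since Section 4.1 has the regimen chosen after individual risk assessment and discussion. Differing practice between sites is a reasonable inference from the text, not something the documents report. The sample size and precision figures are untouched. The case for correction is safety and consistent instruction, and it is sufficient at this cost.

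**What to change.** The sponsor's clinical leads should:

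- reconcile the synopsis (treatment entry and dose row), Sections 4.1, 4.7.2, 4.7.3 and 4.7.5, and Appendix 2 (recommended tests and Dosing), so that each group and each drug class has one instruction;
- state whether the protocol body or Appendix 2 prevails where they differ and, if a departure from the annexed guidance is intended, say so;
- use the same wording wherever an instruction is repeated, and check the Appendix 1 leaflet against it;
- notify all sites.

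Which rule is right is for the clinical leads, and nothing here proposes one. The cost is amendment wording, its submission to the ethics committee under Section 10.1.2, and one site notice. Data collection, sample size and planned analyses do not change.

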1. BACKGROUND AND RATIONALE

In the UK sustained prevention efforts have not reduced the rate of HIV acquisition by men who have sex with men (MSM) [1]. HIV incidence overall in MSM Genitourinary medicine (GUM) clinic attendees remains at about 1.34% annually, and estimates for Black African heterosexuals (0.17% per year) remain higher than for non-MSM populations overall (0.03% per year). The total cost of caring for those living with HIV will rise inexorably as numbers infected increase. New prevention initiatives are needed to reduce the estimated 4,700 incident infections occurring annually, of which 2,800 occur in MSM. Tenofovir containing regimens used as HIV Pre-Exposure Prophylaxis (PrEP) are highly effective at reducing the risk of HIV acquisition [2-4], and PrEP is recommended as an effective component of an active risk reduction intervention by the European AIDS Clinical Society (EACS) [5], the European Centre for Disease Prevention and Control (ECDC) [6], and the World Health Organisation (WHO) [7].

In the UK, the PROUD trial was designed to measure effectiveness when participants were aware they were taking PrEP. It was stopped early as the high HIV incidence in MSM not on PrEP (9% annually) allowed the strength of PrEP effectiveness to be measured sooner than expected [8]. Therefore, while the safety, efficacy and potential effectiveness of oral PrEP are well established, a number of key questions remain and heterosexual patients were not included in the trial. In this context, NHS England led a programme of work to consider how PrEP as an intervention could be planned and commissioned, based on the available data and plausible assumptions about PrEP eligibility, uptake, adherence and duration of use. Subsequently, PHE advised that before PrEP is used on a substantial scale in England, a better option would be to conduct a trial to address current uncertainties in the policy assumptions. A trial would prioritise these questions about the PrEP 'prevention care continuum' and ensure the required answers are obtained.

Proposed PrEP eligibility criteria developed by a multi-disciplinary and multi-stakeholder panel, as revised in October 2016, used the Genitourinary Medicine clinic activity dataset (GUMCAD) to identify the sub-group of MSM with a prior negative HIV test at that clinic in whom HIV incidence was high (3.3% annually) – patient population A , point 2 [9]. The proportion of attendees who had already contracted a bacterial STI (33%) was used to approximate the

proportion thought likely to report condomless sex in the previous 3 months and likely to have repeated condomless sex in the next 3 months (source: GUMCAD, HIV & STI Department, Public Health England, HIV incidence analyses 2012 to 2017). However, there is considerable uncertainty about this approximation for the proportion that would be clinically risk assessed as at high HIV risk and there is competing data from clinic surveys to suggest the proportion could be as high as 60% [10].

The likely uptake of PrEP among those who meet eligibility criteria is unknown, especially when it is recommended to them by a clinician; current estimates are based upon North American experience [10]. It is expected that PrEP users will move in and out of periods of risk and, therefore, may be on PrEP for varying amounts of time, the duration of which is another uncertainty. Using GUM clinic data from 2010 to 2015, the proportion at high-risk in year 1, defined by diagnosis of a bacterial STI in the past year, who remained at high-risk in years 2 through 6 is 27%, 13%, 8%, 5%, and 3%, respectively. Although, this suggests large turnover in those at high risk, this is based on recurrent rates of bacterial STIs and not on history of condomless sex. If the average duration of periods of condomless sex is substantially greater than a year then it would imply a considerable increase in the cumulative numbers of MSM requiring PrEP.

Identifying and engaging individuals in other populations at high risk of HIV, including black Africans and transgender men and women, will be crucial to maximising the potential benefits of PrEP. However, the number of clinic attendees in populations other than MSM who will be deemed as being at high risk of HIV acquisition and eligible for PrEP is unknown.

There is little doubt that, when taken correctly, PrEP can significantly reduce the risk of acquiring HIV for an individual. Nonetheless, when delivered at scale to a population, many factors may influence the impact of PrEP. Investigation of each reported HIV seroconversion in those who begin PrEP within the trial will help to assess the extent of PrEP adherence and provide an indication of effectiveness. Another concern about PrEP use is the potential increase in condomless sex with a consequent increase in bacterial STIs, and there is evidence from other countries that this is happening. Participants in PROUD were already at extremely high risk of HIV and other STIs, so extrapolating from these data may be falsely re-assuring. Those accessing PrEP in a large-scale trial may have a lower STI risk prior to taking PrEP and greater

scope for risk compensation when taking PrEP (compared to PROUD participants). However, given HIV and STI incidence has been monitored using GUMCAD in MSM clinic attendee sub-groups for over five years, the population impact of a large-scale PrEP trial on HIV and bacterial STI incidence will be measured both for those taking and not-taking PrEP and stratified by risk markers.

Therefore, this trial aims to address the outstanding questions agreed between Public Health England, NHS England and professional and community stakeholders. For sufficiently robust answers concerning the components of the PrEP continuum of prevention care (% eligible, uptake, duration, etc.) across the heterogeneity of clinics, clinic attendees and eligibility criteria, a trial size of at least 10,000 person years PrEP is required. To mitigate against future geographical inequity in PrEP provision as many clinics as possible should be recruited to the trial. Trial design, methods and data flows should support regular (i.e. quarterly) 'one-to-one' clinical risk assessments to ensure PrEP is delivered 'as part of an active risk reduction intervention including health education and safer sex promotion' [9].

Essential to any future PrEP programme will be the ability to monitor and audit compliance with eligibility criteria and repeated clinical risk assessments. The central role of the GUMCAD information system to the monitoring and evaluation of PrEP has been endorsed by all stakeholders.

